10.6.4.2. Blood Pressure Endpoints

Blood Pressure Endpoints
Pre- and Post- Dialysis BP

 • For subjects undergoing dialysis in-clinic, both pre- and post- dialysis BP values will be measured. • Unless otherwise specified, for summaries and analyses of BP values, the post-dialysis BP values for subjects undergoing dialysis in-clinic will be used.

CONFIDENTIAL

201410

Blood Pressure Endpoints
End of Treatment BP Value

 See Section 10.6.1.
Mean Arterial Pressure (MAP)

 $MAP = [(2 \cdot DBP) + SBP] / 3$
Blood Pressure Exacerbations

 BP exacerbations will be defined as (≥ 25 mmHg increase from baseline or $SBP \geq 180$ mmHg or $DBP \geq 15$ mmHg increase from baseline or $DBP \geq 110$ mmHg) and grouped by type as follows: 
 BP exacerbations 
 SBP exacerbations 
 ≥ 25 mmHg increase from baseline or $SBP \geq 180$ mmHg 
 $SBP \geq 180$ mmHg and baseline $SBP < 180$ mmHg (including subjects with a missing baseline SBP) $SBP \geq 180$ mmHg and baseline $SBP \geq 180$ mmHg DBP exacerbations 
 ≥ 15 mmHg increase from baseline or $DBP \geq 110$ mmHg 
 $DBP \geq 110$ mmHg and baseline $DBP < 110$ mmHg (including subjects with a missing baseline DBP) $DBP \geq 110$ mmHg and baseline $DBP \geq 110$ mmHg
Notes:

 BP values used to assess BP exacerbations must be on-treatment (see Section 10.4.1), unless otherwise specified. BP values used to assess BP exacerbations can be scheduled or unscheduled. For visits where BP is measured in triplicate, the average of the 3 BP values will be used to assess BP exacerbations. For subjects who have in-clinic dialysis, BP exacerbations identified using post-dialysis BP values will be used in summaries and analyses of BP exacerbations, unless otherwise specified. Subjects with multiple exacerbation events on the same calendar date for each type defined above are considered to have one exacerbation event for event counts by type. For example, a subject with a SBP and a DBP exacerbation on the same date would count in each of the SBP and DBP types, but would only count as one BP exacerbation event in the total BP exacerbation type.
Blood Pressure Exacerbation Event Date

 Date of BP exacerbation
On-Treatment BP Medication

 See Section 10.4.1 for treatment states for concomitant medications.
General

 Censored time (days) = last non-zero dose date treatment start date + 1 BP exacerbation person years = (cumulative total of censoring time for all subjects) / 365.25

CONFIDENTIAL

201410

Blood Pressure Endpoints

 BP exacerbation event incidence rate (per 100 person years) = (100 * number of BP exacerbations) / BP exacerbation person years
Changes in Blood Pressure Medications

 No change: no new anti-hypertensive records since baseline (day before randomized treatment start date) and no change to anti-hypertensive records since baseline until date of visit while on randomized treatment Increase: addition of new anti-hypertensive records for any reason or a change with primary reason for changing dose/frequency or stopping of 'increased to...' since baseline until date of visit while on randomized treatment Decrease: discontinuation of an anti-hypertensive record with primary reason for change starting with "discontinued" or a change with a reason of 'Decreased due to...' since baseline until date of visit while on randomized treatment Switch = change with a reason of 'switched to another agent...' since baseline until date of visit while on randomized treatment
Cumulative Changes in Blood Pressure Medications

 For the summary of cumulative changes excluding "Once only" and "PRN" records, cumulative change will be counted from the date of first randomized treatment to the Week 52 visit date while on randomized treatment. If a new anti-hypertensive medication is added during this time, it will be counted as one change. If the medication also stops during this period, then it will count as two changes (one change due to starting, and one change due to stopping). The cumulative number of changes will be calculated by adding up the changes for all records during this time period. For the summary of cumulative changes for "Once only" records only, cumulative change will be counted from the date of first randomized treatment to the Week 52 visit date while on randomized treatment. Since "Once only" doses will have same start and stop dates, a new anti-hypertensive medication record during this period will be counted as one change. As "once only" doses are likely administered to control BP during dialysis, so they are considered part of a single titration regimen, hence multiple "once only" records on the same date will be counted as one change.

10.6.4.3. Adverse Events

Adverse Events
AEs of Special Interest

Adverse events of special interest are classified as follows:
 
 Thrombosis and/or tissue ischemia secondary to excessive erythropoiesis Death, myocardial infarction, stroke, heart failure, thromboembolic events, thrombosis of vascular access Cardiomyopathy Pulmonary artery hypertension Cancer-related mortality and tumor progression and recurrence Esophageal and gastric erosions Proliferative retinopathy, macular edema, choroidal neovascularization Exacerbation of rheumatoid arthritis Worsening of hypertension

Adverse Events

Potential AESIs will be identified through a pre-defined terms of interest process in which pre-defined lists of AE preferred terms corresponding with each AESI will be used to identify events considered to be potential AESIs. Sites will be prompted via query to complete any necessary additional information for these AESIs in the eCRF.

For the category of thrombosis and/or tissue ischemia secondary to excessive erythropoiesis, after the terms of interest list has been applied, the additional Hgb criteria described below will be applied to identify only those events that are considered to be secondary to excessive erythropoiesis as meeting the AESI definition for thrombosis and/or tissue ischemia secondary to excessive erythropoiesis.


Thrombosis and tissue ischemia events will be considered to be secondary to excessive erythropoiesis if during the window of [AE start date – 30 days, AE start date +15 days] any one of the following 3 events occurs:
 
 • Any Hgb value \geq 13 g/dL (measured pre-dialysis) • Hgb increase $>$ 2 g/dL over 2 weeks (+1 week) 
 ○ Note: for programming purposes, a +1 week window is applied, corresponding to the allowable visit window, to look for increases $>$ 2 g/dL over 3 weeks • Hgb increase $>$ 4 g/dL over 4 weeks (+1 week) 
 ○ Note: for programming purposes, a +1 week window is applied, corresponding to the allowable visit window, to look for increases $>$ 4 g/dL over 5 weeks 
To identify Hgb increases that meet the increase criterion above, all Hgb values taken within [AE start date – 58 days, AE start date + 15 days] will be identified. This corresponds to identifying Hgb values that occurred 4 weeks before the [AE start date – 30 days, AE start date +15 days] window of interest. HemoCue Hgb and central laboratory Hgb values will then be evaluated separately to identify increases, so that HemoCue and central laboratory Hgb values are not compared to each other to identify an increase.
 
For HemoCue Hgb and separately for central laboratory Hgb values, if there is a Hgb value (or daily Hgb average) within the [AE start date – 30 days, AE start date +15 days] window and an earlier Hgb value (or daily Hgb average) that is within the larger [AE start date – 58 days, AE start date + 15 days] window, and the amount of time between the two Hgb values is:
 
 • Between 1 day and 3 weeks, inclusive, then the Hgb values will be compared to determine if there has been a Hgb increase $>$ 2g/dL. • Between 15 days and 5 weeks, inclusive, then the Hgb values will be compared to determine if there has been a Hgb increase $>$ 4g/dL. 
Unscheduled Hgb values will also be used in the assessment of secondary to excessive erythropoiesis following the guidance specified in Section 10.6.3 for unscheduled Hgb values and multiple Hgb values on the same date.

Pre-defined Lists of AE Preferred Terms Corresponding with Each AESI
 
Thrombosis and/or tissue ischemia secondary to excessive erythropoiesis
 
 • Narrow SMQ: Embolic and thrombotic events, arterial

CONFIDENTIAL

201410

Adverse Events	

 • Narrow SMQ: Embolic and thrombotic events, venous • Narrow SMQ: Embolic and thrombotic events, vessel type unspecified and mixed arterial and venous • Broad SMQ: Thrombophlebitis • Additional Preferred Terms: 
 ○ Vascular access site occlusion ○ Vascular access site complication ○ Retinal vascular occlusion ○ Administration site ischaemia ○ Anterior segment ischaemia ○ Application site ischaemia ○ Biliary ischaemia ○ Bone marrow ischaemia ○ Brain stem ischaemia ○ Catheter site ischaemia ○ Cerebellar ischaemia ○ Cerebral ischaemia ○ ECG signs of myocardial ischaemia ○ Gastrointestinal ischaemia ○ Graft ischaemia ○ Hepatic ischaemia ○ Implant site ischaemia ○ Infusion site ischaemia ○ Injection site ischaemia ○ Intestinal ischaemia ○ Ischaemia ○ Macular ischaemia ○ Medical device site ischaemia ○ Myocardial ischaemia ○ Peripheral ischaemia ○ Renal ischaemia ○ Retinal ischaemia ○ Spinal cord ischaemia 	
 ○ Stoma site ischaemia ○ Subendocardial ischaemia ○ Uterine ischaemia ○ Vaccination site ischaemia ○ Vestibular ischaemia ○ Cerebral small vessel ischaemic disease ○ Colitis ischaemic ○ Delayed ischaemic neurological deficit ○ Hypoxic-ischaemic encephalopathy ○ Ischaemic cardiomyopathy ○ Ischaemic cerebral infarction ○ Ischaemic contracture of the left ventricle ○ Ischaemic enteritis ○ Ischaemic gastritis ○ Ischaemic heart disease prophylaxis ○ Ischaemic hepatitis ○ Ischaemic limb pain ○ Ischaemic mitral regurgitation ○ Ischaemic nephropathy ○ Ischaemic neuropathy ○ Ischaemic pancreatitis ○ Ischaemic skin ulcer ○ Ischaemic stroke ○ Necrosis ischaemic ○ Ocular ischaemic syndrome ○ Optic ischaemic neuropathy ○ Reversible ischaemic neurological deficit ○ Transient ischaemic attack

Death, myocardial infarction, stroke, heart failure, thromboembolic events, thrombosis of vascular access
	

 • Death: all fatal SAEs • Myocardial infarction: 
 ○ Broad SMQ: Myocardial infarction ○ Additional Preferred Terms: 
 ▪ Angina pectoris ▪ Anginal equivalent ▪ Cardiac arrest ▪ Chest discomfort ▪ Chest pain ▪ Myocardial ischaemia 	

Adverse Events																			

 
 ▪ Prinzmetal angina ▪ Non-cardiac chest pain • Stroke: 
 ○ Broad SMQ: Conditions associated with central nervous system haemorrhages and cerebrovascular accidents ○ Narrow SMQ: Ischaemic central nervous system vascular conditions ○ Narrow SMQ: Central nervous system vascular disorders, not specified as haemorrhagic or ischaemic • Heart failure: Narrow SMQ: Cardiac failure • Thromboembolic events & thrombosis of vascular access: 
 • Narrow SMQ: Embolic and thrombotic events, arterial • Narrow SMQ: Embolic and thrombotic events, venous • Narrow SMQ: Embolic and thrombotic events, vessel type unspecified and mixed arterial and venous • Broad SMQ: Thrombophlebitis • Additional Preferred Terms: 
 ○ Vascular access site occlusion ○ Vascular access site complication ○ Retinal vascular occlusion 																			
Cardiomyopathy																			

 • Narrow SMQ: Cardiomyopathy 																			
Pulmonary artery hypertension																			

 • High Level Term: Pulmonary hypertensions • Additional Preferred Terms: 
 
 ○ Right ventricular dilatation	○ Right ventricular enlargement	
 
 ○ Right ventricular dysfunction	○ Right ventricular failure	
 
 ○ Right ventricular ejection fraction decreased	○ Right ventricular hypertrophy	
 
 	○ Right ventricular dilatation	○ Right ventricular enlargement	○ Right ventricular dysfunction	○ Right ventricular failure	○ Right ventricular ejection fraction decreased	○ Right ventricular hypertrophy													
○ Right ventricular dilatation	○ Right ventricular enlargement																		
○ Right ventricular dysfunction	○ Right ventricular failure																		
○ Right ventricular ejection fraction decreased	○ Right ventricular hypertrophy																		
Cancer-related mortality and tumor progression and recurrence																			

 • Narrow SMQs: 
 
 ○ Biliary malignant tumours	○ Myelodysplastic syndrome	
 
 ○ Biliary tumours of unspecified malignancy	○ Oropharyngeal neoplasms	
 
 ○ Breast malignant tumours	○ Ovarian malignant tumours	
 
 ○ Breast tumours of unspecified malignancy	○ Ovarian tumours of unspecified malignancy	
 
 ○ Liver malignant tumours	○ Prostate malignant tumours	
 
 ○ Liver tumours of unspecified malignancy	○ Prostate tumours of unspecified malignancy	
 
 ○ Malignancy related conditions	○ Tumour lysis syndrome	
 
 ○ Haematological malignant tumours	○ Skin malignant tumours	
 
 ○ Non-haematological malignant tumours	○ Skin tumours of unspecified malignancy	
 
 	○ Biliary malignant tumours	○ Myelodysplastic syndrome	○ Biliary tumours of unspecified malignancy	○ Oropharyngeal neoplasms	○ Breast malignant tumours	○ Ovarian malignant tumours	○ Breast tumours of unspecified malignancy	○ Ovarian tumours of unspecified malignancy	○ Liver malignant tumours	○ Prostate malignant tumours	○ Liver tumours of unspecified malignancy	○ Prostate tumours of unspecified malignancy	○ Malignancy related conditions	○ Tumour lysis syndrome	○ Haematological malignant tumours	○ Skin malignant tumours	○ Non-haematological malignant tumours	○ Skin tumours of unspecified malignancy	
○ Biliary malignant tumours	○ Myelodysplastic syndrome																		
○ Biliary tumours of unspecified malignancy	○ Oropharyngeal neoplasms																		
○ Breast malignant tumours	○ Ovarian malignant tumours																		
○ Breast tumours of unspecified malignancy	○ Ovarian tumours of unspecified malignancy																		
○ Liver malignant tumours	○ Prostate malignant tumours																		
○ Liver tumours of unspecified malignancy	○ Prostate tumours of unspecified malignancy																		
○ Malignancy related conditions	○ Tumour lysis syndrome																		
○ Haematological malignant tumours	○ Skin malignant tumours																		
○ Non-haematological malignant tumours	○ Skin tumours of unspecified malignancy																		

CONFIDENTIAL

201410

Adverse Events	

 ○ Haematological tumours of unspecified malignancy ○ Non-haematological tumours of unspecified malignancy ○ Malignant lymphomas 	
 ○ Uterine and fallopian tube malignant tumours ○ Uterine and fallopian tube tumours of unspecified malignancy

 ● Additional Preferred Terms: 
 ○ Aplastic anaemia ○ Cytopenia 	
 ○ Pancytopenia ○ Aplasia pure red cell
Esophageal and gastric erosions	

 ● High Level Terms: 
 ○ Duodenal ulcers and perforation ○ Gastric ulcers and perforation ○ Gastrointestinal ulcers and perforation, site unspecified ● Additional Preferred Terms: 
 ○ Haematemesis ○ Gastrointestinal haemorrhage ○ Upper gastrointestinal haemorrhage 	
 ○ Oesophageal ulcers and perforation ○ Peptic ulcers and perforation ○ Helicobacter duodenitis ○ Helicobacter gastritis ○ Melaena
Proliferative retinopathy, macular edema, choroidal neovascularization	

 ● Broad SMQ: Retinal disorders 	
Exacerbation of rheumatoid arthritis	

 ● High Level Term: Rheumatoid arthropathies ● Additional Preferred Terms: 
 ○ Rheumatoid factor increased ○ Rheumatoid factor positive 	

 ○ Rheumatoid factor quantitative increased 	
Worsening of hypertension	

 ● Narrow SMQ: Hypertension 	
Blood Pressure Events	

BP events will be identified during the study via programmatic sweeps of AE and SAE terms entered into the eCRF (using the narrow SMQ for hypertension). AEs identified this way will require an additional BP Exacerbation eCRF page to be completed that characterizes the event as clinically significant and/or symptomatic.
 
In addition, subjects that experience BP values that meet the following criteria at any visit will also be considered to have a BP event and be required to complete the Blood Pressure
	

CONFIDENTIAL

201410

Adverse Events

Exacerbation eCRF page:
 
 • SBP: an increase from baseline of ≥ 25 mmHg or SBP ≥ 180 mmHg • DBP: an increase from baseline of ≥ 15 mmHg or DBP ≥ 110 mmHg
BP-related SAEs are those SAEs that have been identified via the BP Exacerbation eCRF page.
General Definitions

 • Post-Randomization last contact date for censoring (subjects not having AE) will be defined as the study completion date.

 • Treatment emergent last contact date for censoring (subjects not having AE) will be defined as follows: 
 ○ 1 day after last non-zero dose date (last non-zero dose date + 1) for subjects not having treatment emergent AE and continuing on study past (last non-zero dose date + 1) ○ Last non-zero dose date for all other subjects

 • AE Patient Years: (Cumulative total of time to AE for subjects who have the AE + Cumulative total of censoring time for subjects without the AE) / 365.25 
 ○ For treatment emergent AEs, the start date of the patient year value for each subject should be the treatment start date. ○ For post-randomization AEs, the start date of the patient year value for each subject should be the randomization date. ○ For follow-up AEs, the start date of the patient year value for each subject should be 2 days after the last non-zero dose date (last non-zero dose date + 2).

 • Incidence Rate (per 100 patient years): $(100 * \text{Number of subjects with at least 1 AE}) / \text{AE person years}$

 • For the analysis of the time to AE onset/worsening, if the AE onset/worsening date is missing then the time to AE onset/worsening will be counted as 1 day.

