6.11. Anemia Rescue Therapy

A rescue algorithm is provided to minimize subjects having an inadequate response to the treatment for their anemia for an extended period of time and to enable consistency in the application of rescue therapy across the study. Details are provided in [Table 5](#).

This rescue algorithm does not apply to subjects with a low Hgb as a result of an acute or sub-acute event with an identifiable cause (e.g., GI bleed, blood loss due to surgery or vascular access). In these cases, treatment should be directed to the specific cause AND randomized treatment will be continued. If a subject is transfused as part of the treatment, then the randomized treatment will be maintained at the current dose (unless Hgb is ≥ 12 g/dL which requires a dose hold).

Table 5 Rescue Algorithm for Anemia Management

Evaluate Subject for Rescue if: HemoCue Hgb remains <9 g/dL (at a scheduled visit, Week 4 onwards) despite three ¹ consecutive dose increases above the starting dose or post-rescue ² (where HemoCue Hgb<9 g/dL prior to each dose increase) OR HemoCue Hgb is <7.5 g/dL despite a dose increase at the prior study visit.	
Step 1: Initial Intervention	While continuing randomized treatment (increase dose if HemoCue Hgb <7.5 g/dL; otherwise maintain current dose), intervene with one or more of the following as dictated by clinical comorbidities: 
 - Single course of IV iron up to 1000 mg (in addition to the iron management criteria) - Transfusion of up to two units of packed red blood cells (PRBC) if clinically indicated - Allow additional 4 weeks on randomized treatment (NOTE: this is a required choice; can be combined with either or both of the above)
Step 2: Rescue	Check HemoCue Hgb 4 weeks \pm 1 week from last study visit; earlier checks of Hgb may be obtained to advise further intervention as clinically indicated. Randomized treatment should be permanently discontinued and the subject should be rescued according to local clinical practice if either, 
 - HemoCue Hgb remains <9 g/dL despite initial intervention based on the average of two HemoCue Hgb values³ OR - More than two units of PRBC were needed for transfusion (and was not related to acute bleeding).

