12.4. Appendix 4: Benefit:Risk Assessment

Potential Risk of Clinical Significance	Summary of Data/Rationale for Risk	Mitigation Strategy
Daprodustat		
Excessive erythropoiesis (polycythemia) leading to thrombosis and/or tissue ischemia	
In animal studies, excessive erythropoiesis attributed to daprodustat was associated with vascular congestion/inflammation, microthrombi, and tissue ischemia in a number of organs.
 
Phase 2 dose-ranging studies, and associated statistical and exposure response modelling has informed Phase 3 dose rationale, starting doses, dose levels, and dose adjustment scheme to optimize Hgb management.
 
Following review of clinical data received to date, this has not been identified as a safety concern for daprodustat.
	
 • Specific eligibility criteria related to requirements for entry Hgb are detailed in Section 5.1 • Hgb will be closely monitored throughout the dosing period as outlined in the Time and Events Table (Table 6) • Specific guidance for dose adjustment, dose interruption, or discontinuation of daprodustat based on achieved Hgb (including rate of change) is provided in Section 6.2 and Section 6.11 • Unblinded monitoring of safety data by an IDMC in-stream throughout the study.
Death, MI, stroke, heart failure, thromboembolic events, thrombosis of vascular access at Hgb levels which are within the normal range (i.e. not polycythemic conditions)	
Marketed rhEPO and its analogs have been associated with an increased risk for death and serious cardiovascular events when used in patients with anemia of CKD.
 
In non-clinical studies conducted to date, not observed at tolerated doses when hemoglobin/hematocrit within normal range for species.
 
The clinical data received to date are insufficient to conclude or refute this risk.
	
 • Specific eligibility criteria related to CV risk are outlined in Section 5.2 • Hgb will be closely monitored throughout the dosing period as outlined in the Time and Events Table (Table 6) • Unblinded monitoring of safety data by an IDMC in-stream throughout the study

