10.6.3. Efficacy

10.6.3.1. Hemoglobin Endpoints

Hemoglobin Values
Central Laboratory and HemoCue Hgb Values

 When source of Hgb measurement is not specified: 
 For reporting purposes, central laboratory Hgb values will be used, unless otherwise specified. However, if a central laboratory Hgb value is missing, a corresponding non-missing HemoCue Hgb value will be used. This approach will be used for the primary Hgb analysis. Some displays may be created for either central laboratory Hgb values only or HemoCue Hgb values only. The central laboratory summary will be considered the primary summary in this case.
Evaluable Hemoglobin Values

 Evaluable Hgb values are on-treatment Hgb values (see Section 10.4.1.1) that are not taken within the 8 weeks following a red blood cell transfusion, a whole blood transfusion, or a non-randomized ESA treatment which occurs on or after the randomization date. Red blood cell transfusions, whole blood transfusions and non-randomized ESA treatments occurring on or after the randomization date are identified by comparing the start and stop date of the respective transfusion or ESA concomitant medication record to the randomization date.
Imputed Hemoglobin Values

 For each missing value between baseline to Week 52 (inclusive), 200 imputed values will be generated using the multiple imputation method (see Section 7.1.2). The average of these 200 imputed values will be used as the value for this missing value in the summary tables and figures. For the primary efficacy Hgb analysis and the corresponding subgroup analyses using all available observed and imputed Hgb values (on and off-treatment), Rubin's rules [Rubin, 1987] will be used to combine results of the imputed datasets using SAS PROC MIANALYZE procedure.
EP Hemoglobin Value for Primary Hgb Analysis

 For each subject, the mean of all available (on and off treatment) Hgb values during the EP (See Section 10.6.1) including any imputed and unscheduled Hgb values that were taken during this time period. Should the assessment dates for Hgb values from the Early Treatment Discontinuation visit fall within the EP, then these values will be included as unscheduled Hgb values. Hgb values from the Follow-up visit will not be included in the EP mean.

CONFIDENTIAL

201410

Hemoglobin Values					

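### The Hgb-rise criteria for thrombosis/ischemia secondary to excessive erythropoiesis can be met by a transfusion, or by two Hgb values that both follow the event

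*SAP*

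**What the plan says.** SAP 10.6.4.3 first selects thrombosis and ischemia AEs by preferred term. It then applies Hgb criteria whose declared role is to keep only the events regarded as secondary to excessive erythropoiesis. An event is kept "if during the window of [AE start date – 30 days, AE start date +15 days] any one of the following 3 events occurs". The three are an Hgb of at least 13 g/dL, a rise above 2 g/dL over 2 weeks (+1 week), and a rise above 4 g/dL over 4 weeks (+1 week).

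For the rises, "all Hgb values taken within [AE start date – 58 days, AE start date + 15 days] will be identified". The later value must lie between day -30 and day +15. It is compared with an "earlier Hgb value (or daily Hgb average) that is within the larger [AE start date – 58 days, AE start date + 15 days" range. For the smaller rise the permitted gap is "Between 1 day and 3 weeks, inclusive, then the Hgb values will be compared"; for the larger rise it is 15 days to 5 weeks. HemoCue and central-laboratory values are compared only with their own kind. From SAP 10.6.3 the rule imports the handling of unscheduled and same-date values, and nothing else.

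Elsewhere, SAP 10.6.3.1 defines evaluable Hgb as on-treatment values "that are not taken within the 8 weeks following a red blood cell transfusion, a whole blood transfusion, or a non-randomized ESA treatment". Protocol 6.11 (Table 5, Step 1) allows "Transfusion of up to two units of packed red blood cells (PRBC) if clinically indicated" while randomized treatment continues. It also keeps subjects on randomized treatment when they are transfused for an acute cause.

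**The concern.** A rise produced by donor red cells is not erythropoiesis. Nor can a rise measured entirely after onset show that fast erythropoiesis preceded the event. The two rise criteria accept both patterns, at any Hgb level. A subject whose anemia was deep enough to need transfusion can therefore carry a label meant for the opposite state.

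The category matters because "Excessive erythropoiesis (polycythemia) leading to thrombosis and/or tissue ischemia" is the first risk listed for daprodustat in Protocol Appendix 4. SAP 8.2.3.2 reports each AESI by arm, with rates per 100 person-years and relative-risk intervals. If one arm transfuses more, it could appear to have more over-response. The distortion could run in either direction, so it could inflate a daprodustat signal or hide one.

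**Working it through.** **Inputs** (SAP 10.6.4.3; day 0 is the AE start date): later value in days -30 to +15; earlier value in days -58 to +15; gap of 1 to 21 days for a rise above 2 g/dL; gap of 15 to 35 days for a rise above 4 g/dL.

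**The plan's own figure.** The look-back is described as 4 weeks before day -30: 30 + 4 × 7 = 58 days. This agrees with the SAP.

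**The rule applied literally to constructed series.** These are illustrations, not trial data. The last column applies the change proposed below: (a) discount pairs that span a transfusion; (b) require the earlier value on or before day 0.

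| Case | Earlier Hgb (day) | Later Hgb (day) | Transfused (day) | Rise; gap | Flagged now? | Removed by |
|---|---|---|---|---|---|---|
| 1 | 7.2 (-10) | 9.5 (+10) | 0 | 2.3; 20 d | Yes | (a) |
| 2 | 6.8 (+1) | 9.2 (+5) | +2 | 2.4; 4 d | Yes | (a), (b) |
| 3 | 7.0 (-3) | 9.3 (+10) | +1 | 2.3; 13 d | Yes | (a) |
| 4 | 6.9 (-20) | 9.1 (-10) | -15 | 2.2; 10 d | Yes | (a) |
| 5 | 6.5 (+2) | 8.6 (+3) | +2 | 2.1; 1 d | Yes | (a), (b) |
| 6 | 6.9 (-14) | 9.2 (+14) | 0 | 2.3; 28 d | No: above 4 needed | - |
| 7 | 7.0 (-5) | 9.0 (+5) | 0 | 2.0; 10 d | No: not above 2 | - |

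No flagged case reaches 10 g/dL. Cases 2 and 5 show both values after the event; case 1 does not, because its earlier value is at day -10. A rise after the event without any transfusion is removed only by (b), so both parts are needed.

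**What the timing rule permits (rise above 2 g/dL).**
- All day pairs: 46 possible later days × 21 gaps = 966.
- Later value after onset: 15 × 21 = 315 (33%).
- Both values after onset: 15 × 14 / 2 = 105 (11%).

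These count admissible pairs. They are not expected event frequencies.

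**Can the schedule supply such pairs?**
- HemoCue is scheduled two-weekly to Week 8 (Protocol Table 6). Central-laboratory Hgb is scheduled four-weekly.
- From Week 6 visits have a window of ±1 week (Protocol 7), so four-weekly visits can fall 28 - 7 - 7 = 14 days apart.
- The rescue re-check is at 4 weeks ± 1 week, that is 21 to 35 days. Only the 21-day edge meets the smaller-rise limit; at 28 days a rise above 4 g/dL is needed. Protocol Table 5 also allows earlier checks.
- Unscheduled values count.

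**Can a transfusion raise Hgb enough?** The documents give no rise per unit. Assuming 0.7 to 1.3 g/dL per unit, two units give 1.4 to 2.6 g/dL and three give 2.1 to 3.9 g/dL. Two units pass the 2 g/dL threshold only if each adds more than 1.0 g/dL.

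**The case against.** The strongest reply is that a safety screen should favour sensitivity and that few events will be affected. Much of this stands. A flag through a rise needs a listed AE and two trial-captured values by the same method, close together. Protocol 7.4.11 sends non-protocol local laboratory results to source notes, so hospital values before and after a transfusion would generally not enter. Two values within 15 days after onset would come mainly from unscheduled visits or the two-weekly early visits. The AESI tables are descriptive. A separate AESI covers myocardial infarction, stroke and thromboembolic events with no Hgb filter, and adjudicated cardiovascular events are analysed separately (SAP 8.2.2.4).

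A reader might infer that anemic, transfused patients are classified as over-treated, or that everyone transfused near such an AE is exposed. The documents support only that some can be flagged, and over-treatment is not the SAP's term.

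A reader might also want the 8-week evaluable-Hgb exclusion applied to all three criteria. That convention serves the while on-treatment analysis. The primary analysis keeps post-transfusion Hgb (SAP 7.1.2.4), so the SAP does not treat such values as uninformative in general. Applied to the 13 g/dL criterion, the exclusion would take genuine high-Hgb events out of a safety count. That criterion has not been shown to be faulty.

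What the reply does not answer is that the criteria exist to isolate events due to excessive erythropoiesis, and that no other section closes either route.

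**Conclusion.** Wrong as written, with limited reach. The two rise criteria can attribute an event to excessive erythropoiesis when the rise came from a transfusion, or when both values followed onset. This conflicts with the purpose that the same section states. It follows from the text alone and needs no assumption about Hgb per unit.

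The number of affected events cannot be computed, because the documents give no rates for these AEs or for transfusion. Bias between arms depends on transfusion near these AEs differing by arm, which is possible but not shown. The primary and principal secondary tests are untouched; what is affected is a descriptive comparison by arm for one AESI.

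**What to change.** In SAP 10.6.4.3, for the two rise criteria only:

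- (a) Do not count a pair when an RBC or whole blood transfusion occurred on or after the date of the earlier value and on or before the date of the later value.
- (b) Require the earlier value to be on or before the AE start date. The later value may still fall up to day +15, so the nearest measurement after onset remains usable.

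Leave the 13 g/dL criterion unchanged. List by arm the events removed by (a) or (b), and give the count under the present rule as a sensitivity summary.

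The cost is SAP wording and programming before unblinding; transfusion dates are already recorded in the eCRF for subjects on treatment. There are two limits. A genuine rapid response in a subject transfused between the two values would appear in the listing and the sensitivity count, but not in the main count. Part (b) also still admits a rise that began after onset if the earlier value was at or before it. With widely spaced visits that has to be accepted.
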